Hyponatraemia	
Hyponatraemia is categorised by severity based on serum sodium concentrations:
 
• Normal lower limit of serum sodium ≥ 135 mmol/L• Mild hyponatraemia: serum sodium 134-130 mmol/L• Moderate* hyponatraemia: serum sodium < 130 mmol/L• Severe hyponatraemia: serum sodium ≤ 125 mmol/L 
* Moderate hyponatraemia is equivalent to the term ‘clinically significant hyponatraemia’ (Verbalis, 2013)

Nocturnal diuresis	
The nocturnal diuresis rate is calculated from the mean of 3 days Nocturnal Urine Volume (NUV) and total time in bed:
 $\text{Nocturnal diuresis rate (mL/min)} = \frac{\text{NUV (mL)}}{\text{Total Time in Bed (min)}}$
FUSP	
First Undisturbed Sleep Period (FUSP) is defined as the time in minutes from the time of going to bed to the time of first nocturnal void, or time of awakening if no void occurred.

MED	
The lowest dose that has at least a $\Delta=0.3$ larger reduction in mean nocturnal voids as compared to placebo.

ED ₈₅	
The lowest dose that achieves at least 85% of the effect of the maximum dose.

NPi	
Nocturnal Polyuria index (NPi) is calculated by dividing the nocturnal urine volume (NUV) by the 24-hour urine volume (van Kerrebroeck, 2002; Gormley, 2014).
 
In this clinical trial the NPi definition $>33\%$ is used for all ages to define presence of Nocturnal Polyuria (NP).

NUV	
Nocturnal Urine Volume (NUV) is the total urine volume from 5 minutes after bedtime with the intention to sleep until the first void within 30 minutes of rising (in the morning).

Enrichment period	
The enrichment period consists of 1 week active run-in followed by 1 week washout. The enrichment ensures that subjects respond to the drug (reduction in nocturnal diuresis by $\geq 20\%$ from Visit 2 to Visit 3) and have a stable condition of ≥ 2 voids at Visit 2 and Visit 4.

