During the 12 weeks randomised treatment period, any unexpected low serum sodium value (< 135 mmol/L or a drop in serum sodium level > 10 mmol/L) must be re-tested with at least 2 additional consecutive tests to identify the nadir and duration of the hyponatraemic episode. The serum sodium level should be re-tested within 5 (± 2 days) since the previous test. The subject will be followed (by the investigator) for safety until the serum sodium level is stable and not clinically significant, preferably until at least ≥ 135 mmol/L.

Any Time Point during the Trial

If the serum sodium value is ≤ 125 mmol/L at any time point during the trial, the treatment with the IMP must be stopped immediately and the subject must be withdrawn from the trial. All cases of serum sodium values ≤ 125 mmol/L will be reported as Serious Adverse Event (SAEs) (Section 8.5). The subject will be followed (by the investigator) for safety until the serum sodium level is stable and not clinically significant, preferably until at least ≥ 135 mmol/L.

Acute Intercurrent Illness

In case of acute intercurrent illnesses characterised by fluid and/or electrolyte imbalance (such as systemic infections, fever, gastroenteritis), the treatment with IMP should be interrupted until the subject has fully recovered. The treatment can be re-started at the discretion of the investigator once the condition of the subject is stabilised.

In addition, subjects may be called in for additional unscheduled visits due to safety reason, as described in Section 6.8.

Additional Serum Sodium Testing

Events that will trigger additional serum sodium testing include, but are not limited to, the following:

- If more than 21 days elapse from the serum sodium measurement at Visit 1 and the visit date of Visit 2, the serum sodium measurement must be re-tested, with results available prior to Visit 2.
- A subject is presenting with signs or symptoms of hyponatraemia (e.g., headache, dizziness)
- A subject has gained more than 2 kilograms in body weight between visits (Section 7.2.4)
- If concomitant treatment with therapy that may induce hyponatraemia (Section 4.3.1) is initiated or dosing of an existing therapy is increased during the trial, additional serum sodium monitoring should be performed in the first week (4-8 days) after initiation and again with follow-up as judged by the investigator, at least at 4 weeks.

7.1.3.2 von Willebrand Factor and Factor VIII

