9.10.3.1 Hyponatraemia during the Randomised Treatment Period

These analyses are restricted to the Safety Analysis Set only.

The incidence of the post-baseline worst-case hyponataemia episode for each subject will be summarised as described in [Table 9-6](#).

Graphs will plot the serum sodium levels by treatment group and the profiles of the subjects who at any time (Visit 1 and onwards) have a serum sodium level <135 mmol/L will be highlighted.

Kaplan-Meier plots of time from randomisation (Visit 4) to hyponatraemic serum sodium levels (<135, <130 and ≤125 mmol/L) per treatment group will be produced. For the thresholds <135 and <130 mmol/L at least 3 and 2 consecutive observations, respectively, have to be below the threshold to yield a hyponatraemic event ([Table 9-6](#)). For both cases the time is from randomisation until first observation below the respective limit that counts.

The associated relative hazards of treatment and gender will be analysed using Cox proportional hazards model adjusting for baseline serum sodium and age (<65, ≥65 years). Possible heterogeneity between the genders in the relative treatment hazards will be explored by the inclusion of a treatment-by-gender interaction term.

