## 11.2 Safety Endpoints of Special Interest

### 11.2.1 Hyponatraemia Episodes Based on Observed Serum Sodium Levels

#### 11.2.1.1 General Considerations

All tables and figures will be done for the overall trial population and by gender.

Observed serum sodium levels will both be summarized as a continuous variable and be used to define worst-case hyponatraemia episodes using the definitions specified in Table 7.

**Table 7 Definition of Hyponatraemia Episodes by Serum Sodium Range: Number of Consecutive Measurements of Serum Sodium below Upper Threshold Needed to Start Episode**

Degree	Serum Sodium Range (mmol/L)	Enrichment Period	Randomized-Treatment Period	
		Hyponatraemia Episode	Hyponatraemia Episode	'Confirmed' Hyponatraemia Episode
None	≥135	Not applicable (normal serum sodium level)		
Mild	≥130 to <135	1 st observation	1 st observation	3 rd consecutive observation
Moderate	>125 to <130	1 st observation	1 st observation	2 nd consecutive observation
Severe	≤125	1 st observation	1 st observation	1 st observation

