### 11.2.1.3 Hyponatraemia Episodes During the Randomized-Treatment Period based on Observed Serum Sodium Levels

When presenting occurrence (measured as number of subjects) by visit of worst-case hyponatraemia episodes as defined in [Table 7](#), all visits within the same visit window will be combined to define the worst-case hyponatraemia episode observed for the subject within the visit window. The occurrence of worst-case hyponatraemia episodes will be presented by treatment group and visit for the randomized-treatment period for the Safety-RT analysis set.

The number of the post-baseline-ENR ‘worst-case’ hyponatraemia episodes for each subject will be summarized overall and by visit as a categorical variable; here ‘worst-case’ for each episode is defined as the worst-case serum sodium level observed during the hyponatraemia episode.

In addition, the incidence of “Hyponatraemia Episode” ([Table 7](#)) per 1000 person-years at risk counting all events for a subject will be presented overall and by visit using the upper end of the visit window specified for Category I endpoints in [Table 4](#) as cut-points for the categorization of the at-risk time.

For each of the thresholds ( $<135$ ,  $<130$ , and  $\leq 125$  mmol/L), graphs presenting treatment-stratified Kaplan-Meier curves of time from randomization (Visit 4) to first serum sodium level below the threshold will be produced for the Safety-RT analysis set. The time to event is calculated as the date of the first serum sodium level below the threshold minus the date of randomization.

In addition, for the thresholds  $<135$  (mild to severe) and  $<130$  mmol/L (moderate to severe), treatment-stratified Kaplan-Meier plots corresponding to first ‘confirmed’ hyponatraemia episode will be produced. Here the date of confirmation is used as the date of the event. For mild to severe, the date of confirmation is the first of the dates of ‘3rd consecutive observation  $<135$  mmol/L’, ‘2nd consecutive observation  $<130$  mmol/L’, and ‘1st observation  $\leq 125$  mmol/L’. For moderate to

severe, the date of confirmation is the first of the dates of ‘2nd consecutive observation <130 mmol/L’ and ‘1st observation ≤125 mmol/L’.

In Kaplan-Meier plots, all subjects are censored at the earliest of End-of-Trial Visit and 85 days after randomization.

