Since the event times are interval censored (the true time of crossing the threshold was after the time of the preceding serum sodium measurement and before or at the time of the current serum sodium measurement) and essentially grouped by the planned visits, the Kaplan-Meier plots are not quite appropriate. Therefore, event-free-time curves will also be produced based on life table methods using interval cut points derived as 1 + the largest observed event time within each of the visit windows specified for Category I endpoints in [Table 4](#).

Duration of the hyponatraemia episode will be derived as 1 + end date of episode – date of start of episode. For each threshold separately, the duration will be listed for serum sodium episodes defined as one or more observed serum sodium levels below the threshold. The listings will contain the duration, demographics, the day of stop of treatment relative to the start of the hyponatraemia episode, and the serum sodium values observed during the episode including the serum sodium value above 135 mmol/L defining the end of the hyponatraemia episode. For episodes starting before randomization, duration will be listed by sex for all subjects in the Safety-ENR analysis set. For episodes starting after randomization, duration will be listed by sex and treatment group for all subjects in the Safety-RT analysis set experiencing an episode of hyponatraemia based on observed serum sodium levels.

Nadir of observed serum sodium during hyponatraemia episodes will be illustrated by a graph including all hyponatraemia episodes and showing observed serum sodium levels against time since start of the hyponatraemia episode (time zero for an episode is defined as first time point with observed serum sodium below 135 mmol/L in the current episode).

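### SAP 11.2.1.3 ends a hyponatraemia episode only above 135 mmol/L although 135 is normal, and starts a randomised-period episode tally at the run-in baseline

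*SAP*

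**What the plan says.** **End of an episode.** SAP 11.2.1.3 states: "Duration of the hyponatraemia episode will be derived as 1 + end date of episode" minus the start date. It then describes a listing that includes "the serum sodium value above 135 mmol/L defining the end of the hyponatraemia episode". Time zero of an episode is the "first time point with observed serum sodium below 135 mmol/L in the current episode".

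**What counts as normal.** SAP Table 7 grades 135 mmol/L or more as no hyponatraemia, and Protocol Table 9-6 agrees. The protocol's definition of terms gives the "Normal lower limit of serum sodium" as 135 mmol/L or more. Protocol 7.1.3.1 follows a low value "until the serum sodium level is stable and not clinically significant, preferably until at least" that same level.

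**Start of the tally.** Under a heading limited to the randomised-treatment period, SAP 11.2.1.3 says that the number of post-baseline-ENR worst-case "hyponatraemia episodes for each subject will be summarized overall and by visit as a categorical variable". SAP 1.2.1 places baseline-ENR at Visit 2 and baseline-RT at Visit 4. Protocol 9.10.3.1, also headed for the randomised period, has the corresponding summary: "The incidence of the post-baseline worst-case hyponataemia episode for each subject will be summarised".

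**The concern.** Hyponatraemia is the adverse event of special interest (Protocol 8.3) and a named safety endpoint.

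A reading of exactly 135 cannot start an episode and is graded as normal, yet on the SAP's wording it does not end one. That affects more than a listing. The same section counts episodes per subject and computes an incidence per 1000 person-years over all of a subject's events. Recurrent events cannot be counted without a rule for when one episode stops.

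The tally's starting point is a separate matter. Between Visit 2 and Visit 4 every subject takes 500 µg for a week and then washes out. An episode in that interval belongs to the run-in treatment, not to the randomised one, but it enters a summary headed for the randomised period.

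**Working it through.** The documents state no count, duration or power figure that depends on these rules, so there is nothing to reproduce. The check applies the rules literally to illustrative sodium series. These are not trial data, and they assume that a reading of exactly 135 can occur.

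**1. End rule**

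Inputs:
- Duration = 1 + end date − start date, with the start at the first value below 135 (SAP 11.2.1.3).
- Any value below 135 in the randomised period needs at least two further consecutive tests, each within 5 (±2) days of the last (Protocol 7.1.3.1). The nominal 5 days is used here.
- Visits 6, 7 and 8 fall on days 28, 56 and 84.

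| Series (day: mmol/L) | End above 135 | End at 135 or more | Effect |
|---|---|---|---|
| 28: 133, 33: 135, 38: 138 | 1 + 38 − 28 = 11 days | 1 + 33 − 28 = 6 days | +5 days |
| 28: 133, 33: 134, 38: 135, 56: 138 | 1 + 56 − 28 = 29 days | 1 + 38 − 28 = 11 days | +18 days |
| 28: 133, 33: 135, 38: 135, 56: 138 | 29 days | 6 days | +23 days |
| 28: 133, 33: 135, 38: 135, 56: 133, 61: 139, 66: 139 | one episode, 1 + 61 − 28 = 34 days | two episodes of 6 days (28 to 33, 56 to 61) | two counted as one |
| 84: 132, 89: 134, 94: 135, then testing stops | no end date | 1 + 94 − 84 = 11 days | duration cannot be derived |

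The last series meets both the two-test minimum and the protocol's preferred follow-up level.

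**2. Start of the tally**

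- All subjects receive 500 µg between Visits 2 and 3 (Protocol 5.1).
- In the enrichment period one value below 135 is enough for an episode (SAP Table 7).
- A confirmed value below 130 at Visit 3 makes the subject a screening failure (Protocol 7.1.3.1). A value of 130 to 134 does not. Episodes carried into the randomised population are therefore mainly mild or unconfirmed.

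Take 133 at Visit 3 (day −7), 139 at Visit 4 (day 0) and normal values afterwards. The post-baseline-ENR count is 1. The count of episodes starting after Visit 4 is 0.

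**3. Which outputs are exposed**

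- The end rule reaches the duration listings, the per-subject episode count and the all-events incidence.
- The tally start reaches one summary. Its by-visit rows already set Visit 3 apart, so the overall row is the one that mixes periods.
- The tally start does not touch the occurrence table (randomised period, Safety-RT), the Kaplan-Meier curves (from randomisation), the duration listings (split at randomisation) or the therapeutic-window incidences.
- On counts the two rules pull in opposite directions. The end rule can lower a count and the tally start can raise it, so no net bias follows.

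**The case against.** **The wording may only be loose.** The phrase about a value above 135 sits in a sentence describing a listing's contents, and the definitions around it treat 135 as normal. The listing would also print the 135. This is a fair reading of intent. But it is the only statement of how an episode ends, and someone programming from the text would apply it as written.

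**The added time could be overstated.** A reader might infer that a single 135 adds a full 28-day visit interval. The two mandatory re-tests do not support that. At nominal timing after Visit 6 the range is +5 to +23 days, and the upper end needs both re-tests to read exactly 135.

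**Dilution between arms is not shown.** A reader might infer that run-in episodes carried by placebo and low-dose subjects blur the comparison. The sentence on the tally names neither a treatment grouping nor an analysis set, so dilution follows only if the tally is shown by arm. A number can be attached: placebo would reach 50 + 0.2 × 175 = 85 subjects at full enrolment, and 5 to 10% of 85 is about 4 to 9. That percentage is an assumption without support in the documents.

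**A whole-trial count may be intended.** Protocol 9.10.3 does ask for enrichment-period episodes. The limit to the randomised period in Protocol 9.10.3.1 comes from its heading; its explicit restriction is to the Safety Analysis Set. If a whole-trial count is meant, the SAP heading misdescribes it. A slip is at least as likely. SAP 11.2.1.2 uses baseline-RT for sodium change in Safety-RT, and 11.3.1.1 separates adverse events by period. For lowest sodium, SAP 10.4 says baseline-ENR where 10.3.6 and Section 14 say baseline-RT. Section 14 reports other hyponatraemia changes but neither of these.

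**Conclusion.** The point holds as two wording errors in SAP 11.2.1.3, and it is minor. The end rule contradicts the grading in Table 7 and the protocol. Applied literally, it lengthens a duration, leaves it open or merges separate episodes whenever a reading is exactly 135. The tally start puts run-in and washout episodes into the overall row of a randomised-period summary.

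The size is conditional. The first effect needs a reading of exactly 135, and the second needs an episode between Visit 2 and Visit 4; neither frequency is in the documents. The +5 to +23 days assume nominal 5-day re-tests after a low value at Visit 6. The documents do not support a claim that the safety comparison between arms is distorted. No stopping rule or therapeutic-window incidence depends on either rule.

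**What to change.** Make two edits to SAP 11.2.1.3:

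1. Define the analysis end of an episode as the first value of 135 mmol/L or more, consistent with Table 7. This concerns the derivation only and leaves subject follow-up as the protocol has it.
2. In the tally, count episodes starting after randomisation (post-baseline-RT), by actual treatment, for Safety-RT. Tabulate enrichment-period episodes separately for Safety-ENR. If a whole-trial count is wanted, label it as such and split it by period.

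The cost is two wording changes and the matching program specification. No new data are needed.

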### **11.2.2 24-hour Urine Volume**

Observed 24-hour urine volume and the change from baseline-RT will be summarized by visit and treatment group for the Safety-RT analysis set. In addition, change from baseline-RT will be analysed for the using the MMRM approach described in Section [10.3.4](#).

## **11.3 Routine Safety Assessments**

### **11.3.1 Adverse Events**

#### **11.3.1.1 General Considerations**

Adverse events (AEs) are classified according to the latest version of the MedDRA dictionary. The version of MedDRA will be documented.

Written narratives will be issued for all serious AEs (SAE, including deaths) and AEs leading to discontinuation.

Regarding definition of treatment emergent, there are three levels for treatment emergent because of the single-blind enrichment period: pre-treatment, enrichment-treatment emergent, and randomized-treatment emergent. The rules for classification are the following:

- Any AE starting before date of Visit 2 is considered pre-treatment.
- Any AE starting on date of Visit 2 as well as any AE starting after Visit 2, but before date-time for randomization at Visit 4, are considered enrichment-treatment emergent.
- If the subject is not randomized, any AE starting on date of Visit 2 as well as any AE starting after Visit 2 are considered enrichment-treatment emergent.
- Any AE starting after the date-time of randomization at Visit 4 is randomized-treatment emergent.
- AEs with missing start time but starting on date of Visit 4 are considered randomized-treatment emergent.
- AEs with missing start date are considered enrichment emergent.

The total number of subjects reporting an AE, and the percentage of subjects (%) reporting an AE (denominator: number of subjects screened for pre-treatment; number of subjects in the Safety-ENR analysis set for enrichment-treatment emergent; and number of subjects in the Safety-RT analysis set for randomized-treatment emergent) will be presented.

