9.10 Safety

9.10.1 General Considerations

Safety analyses with respect to the enrichment period will be based on the Safety Analysis Set defined for the enrichment period, while analysis with respect to the randomised period will be performed using the safety analysis set.

Safety will be assessed by analysis of adverse events, vital signs, clinical chemistry, haematology, urinalysis and physical examination.

Missing values will be treated as missing, except for causality, intensity, seriousness and outcome of adverse events. A worst-case approach will be used: if causality is missing, the adverse event will be regarded as related to the IMP; if the intensity of an adverse event is missing, the adverse event will be regarded as severe; if seriousness is missing the adverse event will be regarded as serious; if onset date is missing it will be assumed to be the first day of dosing; if outcome is missing and no date of outcome is present the outcome is regarded as 'ongoing'.

Data will be presented in summary tables and listings. Categorical data will be summarised by treatment group using the number and percentage of subjects in each category. For calculation of percentages, the denominator will be the total number of subjects in the respective treatment group

in the safety analysis set. Continuous data will be summarised by treatment group using number of subjects, mean, standard deviation, median, minimum and maximum.

All individual subject data will be listed per subject and treatment as observed including any derived values.

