## 8 Prior and Concomitant Medication

Prior and concomitant medication will be summarized by the Anatomical Therapeutic Chemical Classification System (ATC) classification 1st level (alphabetically), ATC classification 2nd level (in decreasing order of frequency) and treatment group. These medications will be tabulated for the Safety-ENR analysis set according to

- 1) Prior medication taken exclusively prior to any treatment with IMP, i.e., with stop date before the date of dispense of first single-blind IMP;
- 2) Concomitant medication taken during the enrichment period, i.e., medication that was not stopped before the date of first single-blind IMP administration and not started after the date of first double-blind IMP administration;
- 3) Concomitant medication taken during the randomized-treatment period, i.e., medication that was not stopped before the date of first double-blind IMP administration and not started after the End-of-Trial Visit.

If the timing of the dose of a concomitant medication cannot be established in relation to the administration of randomized IMP, it will be considered as concomitant medication in both the enrichment period and the randomized-treatment period.

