#### 11.1.2 Imputation Rules

Missing values will be treated as missing, except for the causality, intensity, seriousness and outcome of adverse events and for the definition of treatment emergent. For adverse events (AEs), a worst-case approach will be used: if causality is missing, the adverse event will be regarded as related to the IMP; if the intensity of an adverse event is missing, the adverse event will be regarded as severe; if seriousness is missing, the adverse event will be regarded as serious; if onset date is missing, it will be assumed to be at the date of Visit 2; if outcome is missing and no date of outcome is present, the outcome is regarded as 'ongoing' at the End-of-Trial Visit.

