**Table 8 Tabulations of Treatment-Emergent Adverse Events**

	Enrichment Period Enrichment Period-Emergent Adverse Events (Safety-ENR Analysis Set)	Randomized Period Randomized- Treatment-Emergent Adverse Events (Safety-RT Analysis Data Set)	Gender-Specific Tabulations
Overview of Adverse Events by treatment group	X	X	
Adverse Events by causality (related/unrelated)	X	X	X
Adverse Events leading to death	X	X	
Adverse Events by intensity		X	X
SAEs	X	X	
Adverse Events leading to discontinuation	X	X	
Adverse Events with an incidence of at least 10% in any treatment group		X	X

	Enrichment Period Enrichment Period-Emergent Adverse Events (Safety-ENR Analysis Set)	Randomized Period Randomized- Treatment-Emergent Adverse Events (Safety-RT Analysis Data Set)	Gender-Specific Tabulations
Adverse drug reactions with an incidence of at least 10% in any treatment group		X	X

Supporting data listings will be provided for:

- All adverse events sorted by site and subject number
- All adverse events sorted by MedDRA Preferred Term
- Serious adverse events
- Adverse events leading to death
- Adverse events leading to discontinuation

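### Adverse events with no start date are all placed in the run-in, even when other information points to onset after randomisation

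*SAP*

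**What the plan says.** SAP 11.1.2 introduces its rules with "For adverse events (AEs), a worst-case approach will be used" and, within that list, says "if onset date is missing, it will be assumed to be at the date of Visit 2". SAP 11.3.1.1 turns the date into a classification: "AEs with missing start date are considered enrichment emergent". Neither sentence carries a condition.

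The neighbouring rules are these:

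- A dated event is placed by its date: "Any AE starting after the date-time of randomization at Visit 4 is randomized-treatment emergent".
- A missing clock time is resolved towards the randomised period: "AEs with missing start time but starting on date of Visit 4 are considered randomized-treatment emergent".
- For medication whose timing relative to randomised treatment is unknown, SAP 8 says "it will be considered as concomitant medication in both the enrichment period and the randomized-treatment period".
- Protocol 9.10.1, in its own worst-case paragraph, says "if onset date is missing it will be assumed to be the first day of dosing". It does not say whether this means the run-in or the randomised period.

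SAP Table 8 has separate columns for the two periods, and the randomised column holds only randomised-treatment-emergent events. SAP 14 lists departures from the protocol and does not mention the choice of Visit 2.

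**The concern.** A subject on randomised treatment may report an event at Week 8 whose start date is never entered. The SAP counts it as having begun before randomisation, on run-in FE 201836, whichever arm the subject is in. It then sits in the enrichment column of Table 8 and is absent from the randomised column, including the rows for serious events and for events leading to discontinuation.

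The randomised-period tables are the only adverse event comparison by randomised dose. A rule described as worst-case would be expected not to take events out of that comparison when information on the form or in the visit record points to the later period.

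**Working it through.** The plan gives no figure on this point, so the check is a reading of the rules followed by two illustrations.

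**1. Where each kind of event goes (SAP 11.3.1.1 and 11.1.2), randomised subject**

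| Information on onset | Period assigned |
|---|---|
| Full date before Visit 2 | Pre-treatment |
| Full date from Visit 2 up to randomisation | Enrichment |
| Full date after randomisation | Randomised |
| Date of Visit 4, time missing | Randomised |
| Date missing, whatever else is known | Enrichment |

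An undated event that truly began after randomisation is removed from the randomised column. One that truly began earlier is never added to it. So the randomised counts can only fall relative to the truth, and the enrichment counts can only rise.

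**2. What other information exists**

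- Protocol 8.2.2 records the date of outcome. A stop date before Visit 4 proves onset before randomisation. A later stop date does not prove later onset, but leaves it open.
- Protocol 6.3 to 6.7 has the subject asked at each of Visits 2 to 8 about events since the previous visit. First report at Visit 6, for example, points to onset after Visit 5.
- The SAP has no rule for partial dates, such as month known and day unknown.

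The SAP rule uses none of this.

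**3. How plausible the default is**

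Inputs: run-in plus washout, 2 weeks; randomised treatment, 12 weeks (SAP 3.1.4); dropout 15% (Protocol 9.1). The documents give no event rate over time, so a constant rate is my assumption.

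- Share of time from Visit 2 that falls after randomisation, for a completer: 12/(12 + 2) = 86%.
- With dropout spread evenly, mean randomised time is 12 × (1 − 0.15/2) = 11.1 weeks, and 11.1/(11.1 + 2) = 85%.
- Adding the 2-week lifestyle period before Visit 2: 12/16 = 75%, or 11.1/15.1 = 74% with dropout.
- Counting only the 1-week run-in: 12/13 = 92%.

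Under that assumption, roughly three quarters or more of undated events in randomised subjects would be expected after randomisation. The rule places none there.

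**4. What one event does to a table**

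SAP 14 expects several FE 201836 groups to have 20 subjects or fewer. Protocol Appendix 2, section 3.1, puts 50 subjects each on placebo and 500 µg at the first interim.

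| Group size | One subject, percentage points |
|---|---|
| 10 | 10.0 |
| 20 | 5.0 |
| 50 | 2.0 |

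Table 8 shows terms reaching 10% in any group. In a group of 20, removing one of two affected subjects takes a term from 2/20 = 10% to 1/20 = 5%. The term then drops out of that table unless another group reaches the threshold. This holds only if the moved event was that subject's sole event under the term.

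**The case against.** **Visit 2 is a defensible choice.** It keeps an undated event from being treated as pre-treatment and charges it to the highest FE 201836 dose, which is conservative for the drug's overall profile. It is also a natural reading of the protocol's wording, since the first dose in the trial is the run-in dose. This stands. A reader might infer that the SAP departs from the protocol, but the protocol is ambiguous and the SAP took one of its two readings.

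**No bias in favour of the drug is shown.** A reader might infer that the rule flatters FE 201836 against placebo. It applies equally to placebo and desmopressin, treatment is double-blind, and nothing in the documents suggests that dates go missing more often in one arm. Counts fall in each arm, but the contrast has no known direction.

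**The therapeutic window is unaffected.** A reader might infer that the dose decision is at stake. SAP 10.4 builds the window from efficacy and serum sodium, and SAP 13 bases risk-benefit on those graphs. Sodium samples carry their own dates, and under Protocol 8.2.2 a laboratory adverse event takes the sample date as its onset.

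**The events are not lost, and they should be few.** They remain in the enrichment tables and in the listings of all events. Serious events and those leading to discontinuation also get narratives. The log requires an onset date and lets only the time be omitted. All of this stands and limits the impact.

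**The medication rule is not a strict precedent.** Counting a medication in both periods affects only a descriptive table. Doing the same for adverse events would count one event twice. The closer parallel is the missing start time on the day of Visit 4, which SAP 11.3.1.1 already resolves towards the randomised period.

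None of these arguments gives a reason to ignore a partial date or visit of first report that places the event after randomisation.

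**Conclusion.** The point holds as a defect in a classification rule. For randomised subjects, SAP 11.1.2 and 11.3.1.1 can assign an event to the wrong period despite evidence to the contrary. Calling the approach worst-case is accurate only against the pre-treatment category.

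The effect is confined to the adverse event tables by period and arm. The documents give no expected number of undated events, and it is probably small. One such event is worth 5 percentage points in a group of 20 and 2 points in a group of 50. The primary analysis, the hyponatraemia analyses and the therapeutic window do not depend on it. This is a cheap improvement.

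**What to change.** Before database release, replace the last classification rule in SAP 11.3.1.1. For a randomised subject, an adverse event with a missing start date is randomised-treatment emergent unless the stop date, partial date or visit of first report shows that it began before randomisation. If the available information shows onset before Visit 2, classify it as pre-treatment. Keep the Visit 2 rule for subjects who were never randomised.

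Three consequential edits follow:

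- Align SAP 11.1.2, so that the imputed onset falls in the assigned period. The date of Visit 4 would serve for events assigned to randomised treatment.
- Add a sentence on partial dates, and name the source for the visit of first report, which is not among the log items in Protocol 8.2.2.
- State which first day of dosing Protocol 9.10.1 means, and record the choice in SAP 14.

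The cost is a few sentences and a small programming change, with no new data and no effect on sample size. The downside is that a run-in event with no other timing information may be counted in the randomised period. A listing of all undated events, with the period assigned and the reason, would let a reader judge this.
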